8.2 Data collection

Designated investigator staff will enter the data required by the protocol into the OC/RDC system. Designated investigator site staff will not be given access to the system until they have been trained.

Automatic validation procedures within the system check for data discrepancies during and after data entry and, by generating appropriate error messages, allow the data to be confirmed

or corrected online by the designated investigator site staff. The Investigator must certify that the data entered into the electronic Case Report Forms are complete and accurate. After database lock, the investigator will receive copies of the patient data for archiving at the investigational site.

8.3 Database management and quality control

Novartis staff (or CRO working on behalf of Novartis) review the data entered into the CRFs by investigational staff for completeness and accuracy and instruct the site personnel to make any required corrections or additions. Queries are sent to the investigational site using an electronic data query. Designated investigator site staff is required to respond to the query and confirm or correct the data. If the electronic query system is not used, a paper Data Query Form will be faxed to the site. Site personnel will complete and sign the faxed copy and fax it back to Novartis staff that will make the correction to the database. The signed copy of the Data Query Form is kept at the investigator site.

Concomitant medications entered into the database will be coded using the WHO Drug Reference List, which employs the Anatomical Therapeutic Chemical classification system. Concomitant procedures, non-drug therapies and adverse events will be coded using the Medical dictionary for regulatory activities (MedDRA) terminology.

Laboratory samples will be processed centrally and the results will be sent electronically to Novartis (or a designated CRO).

ECG readings will be processed centrally and the results will be sent electronically to Novartis (or a designated CRO).

Randomization codes and data about all study drug(s) dispensed to the patient and all dosage changes will be tracked using an Interactive Response Technology (IRT). The system will be supplied by a vendor, who will also manage the database. The database will be sent electronically to Novartis (or a designated CRO).

Each occurrence of a code break via IRT will be reported to the clinical team and monitor. The code break functionality will remain available until study shut down or upon request of Novartis.

8.4 Data Monitoring Committee

A data monitoring committee (DMC) may review the safety data of this trial at selected time intervals. If needed, details regarding the DMC process will be available in relevant secukinumab DMC charter.

8.5 Adjudication Committee

Not required.

9 Data analysis

Treatment groups for analysis will include:

- Secukinumab 150 mg fixed interval

- Secukinumab 300 mg fixed interval
- Secukinumab 150 mg start of relapse
- Secukinumab 300 mg start of relapse
- Secukinumab 300 mg open-label
- Secukinumab 300 mg open-label switch

9.1 Analysis sets

Randomized set: The randomized set will be defined as all subjects who were randomized in core studies and who entered this extension study.

Full analysis set (FAS): The FAS will be comprised of all subjects entered the study. Following the intent-to-treat principle, subjects will be analyzed according to the treatment assigned to at randomization in core study. If the actual stratum is different to the assigned stratum in IRT, the actual stratum will be used in analyses.

Safety set: The safety set includes all subjects who took at least one dose of study treatment during the treatment period. Subjects will be analyzed according to treatment received.

9.2 Patient demographics and other baseline characteristics

Demographics and baseline characteristics

Summary statistics will be presented for continuous demographic and baseline characteristic variables for each treatment group and for all subjects in the randomized set. The number and percentage of subjects in each category will be presented for categorical variables for each treatment group and all subjects.

Medical history

Any significant prior or active medical condition at the time of signing informed consent will be coded using the MedDRA dictionary. These medical conditions will be summarized by primary system organ class and preferred term.

To establish a baseline level of cardiovascular risk, the number and percentage of subjects with pre-solicited cardiovascular risk factors will be summarized by treatment group. The number of cardiovascular risk factors that each subject has will also be summarized by treatment group. If it is unknown whether or not a subject currently or previously experienced a specific cardiovascular risk factor, it will be assumed that cardiovascular risk factor did not occur for that subject.

Psoriasis specific medical history will be summarized by treatment group. Previous treatments for psoriasis and whether or not response was achieved will be summarized by treatment group.

All the medical history information will be retrieved from the core studies.

9.3 Treatments

Study treatment

The analysis of study treatment data will be based on the safety set.

The duration of exposure to study treatment will also be summarized by treatment group. In addition, the number and percentage of subjects with cumulative exposure levels (e.g., any exposure, <4 weeks, \geq 4 weeks, \geq 8 weeks, etc.) will be presented.

Prior and concomitant medication

Prior and concomitant medications will be summarized in separate tables by treatment group.

Prior medications are defined as treatments taken and stopped prior to first dose of study treatment. Any medication given at least once between the day of first dose of randomized study treatment and the date of the last study visit will be a concomitant medication, including those which were started pre-baseline and continued into the period where study treatment is administered.

Medications will be presented in alphabetical order, by Anatomical Therapeutic Classification (ATC) codes and grouped by anatomical main group. Tables will show the overall number and percentage of subjects receiving at least one treatment of a particular ATC code and at least one treatment in a particular anatomical main group.

Significant prior and concomitant non-drug therapies and procedures will be summarized by primary system organ class and MedDRA preferred term.

The number and percentage of subjects receiving different classes of prior psoriasis therapy (biologic systemic therapy, non-biologic systemic therapy, topical, phototherapy, photochemotherapy) will be presented by treatment group as well as the reasons for stopping their previous prior psoriasis therapies (primary lack of efficacy, secondary lack of efficacy, lack of tolerability, other) and the total duration of exposure to psoriasis therapies previously.

Prior concomitant medications will be retrieved from the core studies.

9.4 Analysis of the primary and key secondary variable(s)

The primary analysis will focus on safety variables, please refer to [Section 9.5.2](#). There are no other key secondary variables assessed in this study.

9.4.1 Variable(s)

Not Applicable

9.4.2 Statistical model, hypothesis, and method of analysis

Not applicable

9.4.3 Handling of missing values/censoring/discontinuations

Missing values in efficacy analyses, except for maintenance of response will not be imputed. All analyses will be based on observed values only.

For maintenance of response, please see definition below, missing values with respect to response variables based on PASI score score will be imputed with non-response regardless to the reason for missing data (e.g. premature study discontinuation, missed visit, administrative issues). Following the intent-to-treat principle for subjects who prematurely discontinue treatment, but who are observed in the follow-up period, efficacy data collected in follow-up periods will be linked to planned but missed study visits as well, following imputation schemes described in the analysis plan.

Subjects who opt to change treatment regimen or dose level and move into open-label treatment with 300 mg s.c. secukinumab every four weeks for the remainder of the trial will be considered as non-responders in the analysis of maintenance of response.

For other efficacy analyses they will not be considered after the timepoint of switching.

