Subjects from the CAIN457A2304 maintenance period will continue the treatment regimen and dose that they were assigned to (Fixed interval regimen or Retreatment at start of relapse regimen) during the maintenance treatment period of the core study and return for visits every four weeks up until Week 156. Subjects and study personnel will remain blinded during the first two years of the treatment period (except for patients in the open label part of the study). The last blinded dose of the treatment period is administered at Week 152.

At Week 156, subjects will be unblinded and will have the option (based on investigator judgment) to switch dosing regimens, with the specific options depending on the blinded treatment assigned until that point. Generally, subjects may switch off of the SoR treatment regimen to active secukinumab treatment every four weeks, and subjects may switch from secukinumab 150 mg s.c. to secukinumab 300 mg s.c. After Week 156, office visits will only be required every 12-16 weeks until Week 260 (End of Treatment period for CAIN457A2304E1) unless a subject continues with the SoR treatment regimen. Specific details of the open-label treatment options for unblinded subjects starting at Week 156 are described in Section 5.2 and in Table 5-1.

Subjects from the CAIN457A2307 maintenance period will continue in the treatment regimen and dose that they received during the CAIN457A2307 maintenance treatment period (i.e., 300 mg sc secukinumab every four weeks), and return for visits every four weeks up until Week 156. After Week 156, subjects will continue being treated every four weeks, but will only be required to come in for office visits every 12-16 weeks. These subjects were treated open-label during the core study, and will continue to be treated open-label during the treatment period of CAIN457A2304E1. The last dose of secukinumab is provided at Week 256, four weeks prior to the end of the treatment period.

Please refer to [Section 5.2](#) for a more detailed description of the treatment arms.

Subjects who discontinue study treatment prematurely during the treatment period should have all Week 260 protocol assessments (EOT) performed approximately four weeks after their last dose of secukinumab/secukinumab placebo and then enter the treatment-free follow-up periods (follow-up period and follow-up 2 period).

Follow-up period (for all subjects)

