Retreatment at start of relapse regimen – “SoR” “start of relapse”: either 150 or 300 mg s.c. secukinumab in PFS: “Start of relapse” will be defined as a loss of $\geq 20\%$ of the maximum PASI gain achieved during the CAIN457A2304 or CAIN457A2304E1 study, compared to baseline of the CAIN457A2304 study, *and* a loss of PASI 75 response. Whenever a subject fulfills the start of relapse criteria, active secukinumab will be administered at their scheduled visits (i.e., every four weeks) until the subject is back to PASI 75 response, at which point in time they will start receiving placebo again. The dose administered in the treatment period of this extension study (secukinumab 150 mg or 300 mg in PFS) will be identical to the dose that these subjects received during the maintenance period of the CAIN457A2304 core study. If a subject does not fulfill the criteria of a start of relapse or is back to PASI 75 response after a start of relapse, they will receive placebo PFS injections (two injections per dose) to maintain the blind. This treatment regimen is applied every four weeks, from Week 52 up to and including Week 152.

At Week 156, patients from the maintenance period of the CAIN457A2304 core study will be unblinded and continue in the study on one of the treatment options in [Table 5-1](#) according to investigator judgment for their assigned treatment arm.

Table 5-1 Open-label treatment options starting at Week 156

Previous treatment arm through Week 152 (Unblinded at Week 156)	Treatment options, as decided by the investigator	New office visit frequency
Secukinumab 300 mg FI	Continue secukinumab 300 mg FI	Every 12-16 weeks
Secukinumab 300 mg SoR	Continue secukinumab 300 mg SoR for remainder of the study OR Switch to secukinumab 300 mg dosed every 4 weeks	Every 4 weeks Every 12-16 weeks
Secukinumab 150 mg FI	Continue secukinumab 150 mg FI OR Switch to secukinumab 300 mg dosed every 4 weeks	Every 12-16 weeks Every 12-16 weeks
Secukinumab 150 mg SoR	Continue secukinumab 150 mg SoR for remainder of the study OR Switch to secukinumab 300 mg dosed every 4 weeks	Every 4 weeks Every 12-16 weeks

Open-label treatment arm for subjects entering from the CAIN457A2307 core study

Secukinumab 300 mg s.c. in PFS regimen arm: Each subject to continue receiving two s.c. injections of 150 mg secukinumab in PFS every four weeks. Doses will be administered from Week 52 up to and including Week 256.

Overview of treatment schedule according to treatment arm

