6.4 Efficacy

All efficacy assessments should be performed prior to administration of study treatment.

It is important to **perform the IGA before the PASI**, as the knowledge of PASI scoring can potentially influence how the evaluator scores the IGA. Therefore, the following order should be applied when performing the efficacy assessments during study visits:

- Investigator's Global Assessment (IGA mod 2011; scale from 0 – 4)
- Psoriasis Area and Severity Index (PASI; score from 0 – 72)
- Rebound assessment

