9.5 Analysis of secondary variables

9.5.1 Efficacy variables

Maintenance of response

Maintenance of response will be defined analogously as in the primary endpoint in CAIN457A2304, but for week 104 and 156, i.e. PASI 75 response

- at Weeks 104 and 156, for subjects in the fixed interval regimens, or
- at Weeks 92 and 144, for subjects in the retreatment at start of relapse regimen who do not require active treatment at Week 92 or 144, respectively, or
- at Weeks 104 and 156, for subjects in the retreatment at start of relapse regimen who do require active treatment at Week 92 or 144, respectively.

Summary statistics for maintenance of response at Week 104 and 156 will be presented in contingency tables and will include absolute and relative frequencies. Confidence intervals for response rates will be derived as well based on the score method including continuity correction ([Newcombe 1998](#)).

PASI 50, PASI 75, PASI 90, PASI 100 and IGA 0 or 1 response over time

Summary statistics for PASI 50, PASI 75, PASI 90, PASI 100 and IGA 0 or 1 response by visit will be presented in contingency tables and will include absolute and relative frequencies. Confidence intervals for response rates will be derived as well based on the score method including continuity correction ([Newcombe, 1998](#)).

PASI score over time

Summary statistics will be provided for absolute PASI scores as well as for percent change from baseline by visit and treatment group. Figures will also be provided.

IGA mod 2011 score over time

Summary statistics for the IGA mod 2011 score over time will be presented by visit and treatment group in contingency tables.

Relapse

The number and percentage of subjects experiencing relapse will be presented by visit and treatment group.

Rebound

Rebound is defined as a worsening of PASI of > 125% of the value at baseline (core study), or new pustular, erythrodermic or more inflammatory psoriasis occurring within 8 weeks of stopping therapy (i.e., if this definition is fulfilled at more than 8 weeks after last study treatment administration, this is not defined as rebound). The number and percentage of subjects experiencing rebound will be presented by visit and treatment group.

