### **1.1.1 Changes to statistical methods planned in the protocol**

Table 1-11 is a modified version of table 6-3 of the protocol to clearly indicate that the area score is derived from area% without rounding.

For the maintenance of response analysis, the non-responder imputation method defined in the protocol will be dropped. The as observed result for PASI and IGA responses will be primarily looked into; the multiple imputation method will be provided as well. Assessment during follow-up period excluded.

In addition to the planned analysis on adverse events, by 1-year interval analysis on the adverse events will be provided in order to assess the occurrence of adverse events over time.

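### Protocol 9.4.3 fails Week 156 switchers on maintenance of response although every scheduled endpoint PASI precedes the switch; the SAP probably drops the rule without naming it, and Table 1-2 gives no result by assigned arm

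*Protocol*

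**What the plan says.** **Endpoint.** Protocol 9.5.1 reads PASI 75 at Weeks 104 and 156 in the fixed-interval arms. For start-of-relapse subjects it reads "at Weeks 92 and 144, for subjects in the retreatment at start of relapse regimen who do not require active treatment" at those visits, and Weeks 104 and 156 for the others. The first secondary objective (protocol 2.2) compares SoR with FI within each dose.

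**Switch.** Protocol 3.1: "At Week 156, subjects will be unblinded and will have the option (based on investigator judgment) to switch dosing regimens". The same section adds: "The last blinded dose of the treatment period is administered at Week 152". Protocol 6.4 fixes the order within a visit: "All efficacy assessments should be performed prior to administration of study treatment". In Table 5-1 (protocol 5.2) the only entry for the 300 mg FI arm is "Continue secukinumab 300 mg FI". The 150 mg FI, 150 mg SoR and 300 mg SoR arms may all move to 300 mg every four weeks.

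**Switcher rule.** Protocol 9.4.3 first imputes missing PASI responses as non-response for this endpoint. A separate paragraph then says that subjects who change to open-label 300 mg "will be considered as non-responders in the analysis of maintenance of response". It sets no condition on the observed PASI and no time limit. The sentence after it, on other efficacy analyses, excludes these subjects only from the point of switching onward.

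**SAP.** Section 1.1.1 states that, for this endpoint, "the non-responder imputation method defined in the protocol will be dropped". Observed results come first and multiple imputation second, and section 1.8.4 repeats this. Section 1 still says that data are analysed according to protocol section 9. Table 1-2 marks maintenance of response for eight groups, three of them switch groups. It leaves the combined 150 mg FI column unmarked for this endpoint and has no combined SoR column at all.

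**The concern.** A switch made at Week 156 cannot have influenced a PASI scored earlier, or scored before dosing at that same visit. Calling the switcher a failure therefore records the investigator's decision, not loss of response. That decision was not neutral: protocol 3.3 explains the switch option by the core-study findings that SoR was not shown non-inferior and that 300 mg worked better.

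The rule also acts unequally. At 300 mg only the SoR arm can lose responders; at 150 mg each arm loses them according to its own switching.

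A second problem remains if the rule is ignored. Grouping subjects by switch status sorts them by something decided at or after the last endpoint visit, by an investigator who knows how the subject has done (protocol 5.3). Anyone in a switch group must also have stayed in the study to Week 156. SoR and FI columns built this way are no longer the arms that the objective compares.

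**Working it through.** **1. Timing.** Weeks from each endpoint visit to the switch option at Week 156:

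| Endpoint visit | Weeks before Week 156 |
|---|---|
| 92 | 156 − 92 = 64 |
| 104 | 156 − 104 = 52 |
| 144 | 156 − 144 = 12 |
| 156 | 0, PASI scored before the dose |

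No scheduled endpoint PASI follows a switched dose. One minor exception concerns unscheduled assessments. The SAP window for Week 156 is Day 1080 to 1107 around Day 1093, and the closest assessment is used. If the visit fell on Day 1088 (the early end of ±5 days), an unscheduled PASI on Days 1089 to 1097 would be nearer the target and would displace it, possibly after a switched dose.

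**2. Planned arm size.** Protocol 9.7 gives about 740 entering and about 148 per arm. These reproduce: 918 × 0.95 × 0.85 = 741.3, and 918 × 0.95 × 0.80 × 0.85 / 4 = 148.3. The documents state no figure for maintenance of response or for the number who switch.

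**3. Effect of the rule on an assigned arm, applied literally.** Loss = (share of the arm switching) × (response rate among switchers). This equals p × s, where p is the arm's observed response rate and s is the share of its observed responders who switch. The counted rate is p × (1 − s). Both p and s below are assumptions; n = 148, with counts rounded to whole subjects.

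| p (observed responders) | s = 10% | s = 25% | s = 50% |
|---|---|---|---|
| 0.80 (118) | 107 (72.3%) | 89 (60.1%) | 59 (39.9%) |
| 0.50 (74) | 67 (45.3%) | 56 (37.8%) | 37 (25.0%) |

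In 300 mg FI, s = 0 and the loss is 0.

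Take equal observed rates in 300 mg SoR and 300 mg FI. An unpooled 95% interval for the difference would exclude zero once s reaches about 12% (p = 0.80), 16% (p = 0.70) or 23% (p = 0.50). For p = 0.80 and s = 0.123 the counted rate is 0.7016 and the difference 0.0984. The standard error is √[(0.80 × 0.20 + 0.7016 × 0.2984)/148] = 0.0500, and 1.96 times the unrounded value is 0.0979.

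**4. Effect under the as-observed method.** Observed responders stay responders, so the loss in step 3 is 0.

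**5. Effect of splitting by switch status.** If a share w switches with response rate r, the non-switched rate is (arm rate − w × r)/(1 − w). Assume an arm rate of 0.80, w = 0.30 and r = 0.60. Then (0.80 − 0.18)/0.70 = 0.886. Table 1-2 would show 88.6% and 60% for an arm whose rate is 80%. Beside a 300 mg FI arm also at 80%, the non-switched column would look 8.6 points better through selection alone. The sign reverses if switchers respond better than the rest; the documents do not say which applies.

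**The case against.** The strongest reply is that the SAP has already removed the rule. Section 1.1.1 drops the protocol's non-responder method for exactly this endpoint, and the switcher sentence sits in the same protocol section. An as-observed analysis keeps a Week 156 responder as a responder. The one non-responder imputation that SAP 1.8.1 retains is for a Week 92 or 144 dosing record without a matching PASI, and it does not concern switchers. Table 1-2 points the same way, since three switch columns fixed at 0% would serve no purpose. The rule could also be read as covering only data after the switch, in which case it is redundant.

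Most of this stands. What it does not settle is that SAP 1.1.1 speaks of imputation, whereas a switcher's Week 156 PASI is observed and the protocol treats switchers in a paragraph of their own. Because SAP section 1 refers back to protocol section 9, a programmer could defend either reading.

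A reader might infer that the final analysis will turn observed responders into failures, with a loss of tens of percentage points in the switchable arms. The documents do not support that. The primary presentation is as observed, and the switching share and switchers' response rate are unknown. Even if the rule were applied, Table 1-2 would put the zeros in the switch columns and leave the non-switched SoR column unchanged. An example with 50% switching, 60% of them responding and an arm rate of 80% gives a loss of 0.5 × 0.6 = 30 points. It also requires every non-switcher to respond: (0.80 − 0.30)/0.50 = 100%.

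It is also fair to say that this is a secondary, descriptive endpoint. Safety is primary (protocol 2.1 and 9.4), and SAP 1.8.3 plans no hypothesis test.

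**Conclusion.** The concern holds in a limited form. As written, protocol 9.4.3 can only do nothing or overwrite observed responders, and it can do so in three of the four randomised arms. The SAP probably supersedes it but leaves this to inference. The firmer gap is in Table 1-2: the SoR-versus-FI comparison by assigned regimen, the first secondary objective, is not produced for maintenance of response.

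The size cannot be fixed from the documents. If the rule were applied to assigned arms, the loss would be p × s in 150 mg FI, 150 mg SoR and 300 mg SoR and 0 in 300 mg FI; under the as-observed method it is 0 throughout. The illustrations rest on assumed rates and the planned 148 per arm. Protocol 3.1 reports 675 enrolled against about 740 expected, so actual arms are likely to be smaller. No alpha, power or primary safety conclusion is touched.

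**What to change.** Make the change in the SAP; no protocol amendment is needed to settle the analysis.

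- In SAP 1.1.1 and 1.8.4, state that the switcher rule of protocol 9.4.3 does not apply to maintenance of response.
- In the same place, state that observed PASI up to and including the pre-dose Week 156 assessment counts under the regimen assigned up to Week 156. This also closes the unscheduled-assessment exception in the Week 156 window.
- In Table 1-2, report maintenance of response for the four assigned arms, with switched and non-switched subjects combined. Keep any split by switch status as descriptive only.

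The cost is one or two SAP sentences and one added set of columns. No new data are needed.
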